### 4.3. Device Issuance and Replacement

SenoClaire® - GE Breast Tomosynthesis (DBT), FFDM, and IDI MammoWorkstation devices used in this study are commercially available. Unique identifying information (e.g. model, serial number, etc.) of each device used in this study will be recorded.

Ancillary equipment, including safety equipment such as protective vests, and surgical equipment necessary for biopsy(ies) procedure(s) will be used in this study according to the

standard of care at the investigational site. These devices will be owned and maintained by the investigational site.

Sites will be encouraged to use equipment owned by the site, if available. For sites that do not own required mammography equipment (DBT, FFDM, and/or IDI MammoWorkstation) or component software versions necessary to complete study procedures, the Sponsor may provide devices for study use.

#### **4.3.1. Maintenance of Research Devices**

Devices used in this study will be maintained, calibrated, and ensured to be functioning correctly during the study, in accordance with applicable site policy and state and federal requirements. The Site Principal Investigator (PI) should inform the Sponsor of any known or anticipated issues with device functionality or availability that could impact the conduct or outcomes of this research study.

#### **4.3.2. Concurrent Use of Research Devices**

The DBT and FFDM devices used in this study are commercially available, multiple-use devices. Devices owned by the site may be used concurrently in this research and for standard of care procedures outside of this study. Devices provided to the site by GE shall be limited to use for mutually agreed upon research projects. The site is responsible for completing routine care, such as prevention of cross-contamination, between procedures that could impact study subjects.

#### **4.3.3. Device Software and Configuration Management**

The most current commercial configuration and software version for SenoClaire® - GE Breast Tomosynthesis (DBT) will be used during this study, and the site(s) should use an IDI MammoWorkstation with software version 4.7 MR2 or higher (capable of viewing V-Preview images). In the event of commercial release of software versions or configuration changes that will be implemented on devices used in this study, changes shall not increase risk classification of the study. The site Principal Investigator (PI) is responsible for notifying the Sponsor of any current or planned software or configuration changes, including the date of implementation on a per-device basis. The Sponsor may, at its discretion or upon site request, require additional training or quality control procedures (e.g. calibration or other routine engineering maintenance activities) following software or configuration changes.

### **4.4. Disposition of the Device/Product**

Devices and associated accessories provided to the site for the purposes of this clinical trial will be collected at the end of the study and returned to GE Healthcare as dictated by mutually agreed terms.

## 5. OBJECTIVES OF RESEARCH STUDY

### 5.1. Hypothesis

No statistical hypothesis is tested in this data collection study. The sample size for DBT-screened women who are ultimately referred for breast biopsy in this study is determined to provide sufficient accrual of cancer cases for a subsequent statistically powered analysis as part of a separate protocol (ADAPT-BIE).

### 5.2. Study Objectives

#### 5.2.1. Primary Objective(s)

The aim of this recruitment plan (ADAPT-Enrich) is to collect image and technical data on both digital breast tomosynthesis (DBT) and full-field digital mammography (FFDM), along with other subject data including histology results from biopsy specimen examination and cancer classification data, from initially asymptomatic women referred for biopsy after recall from DBT screening and diagnostic work-up. These data will be included in a subsequent and prospectively planned pooled analysis to be described in a separate protocol (ADAPT-BIE) examining superiority of DBT to FFDM for breast cancer diagnosis and other clinical performance measures.

#### 5.2.2. Secondary Objectives

An additional aim is to describe cancer and non-cancer cases identified in this accrual study based on histology findings and lesion type.

### 5.3. Study Endpoints

#### 5.3.1. Primary endpoints

The primary endpoint will be the site's diagnosis for each subject of cancer status (positive or negative/benign) based on histopathology of biopsy/surgical findings and histologic concordance with imaging for benign lesions.

#### 5.3.2. Secondary Endpoints

Secondary endpoints for all subjects will include histology findings and size, lesion type, and other lesion characteristics based on image appearance. Technical characteristics of electronic image data collected from subjects, such as information related to radiation dose, may be extracted and analyzed by the Sponsor for the purposes of this study.

#### 5.3.3. Safety endpoints

Device-related adverse events (AEs), serious adverse events (SAEs), and device malfunctions by overall occurrence and imaging modality (DBT and FFDM) that occur during the study will be collected. No other clinical safety assessments will be performed.

## 6. DESIGN OF RESEARCH STUDY

[figure not shown]
### 6.1. Type of Research Study

#### 6.1.1. Study Type

This study (ADAPT-Enrich) is an open-label, multi-center, within-subject crossover, prospective, clinical research study, collecting images and associated data from bi-lateral two-view DBT and FFDM exams conducted with GE systems. Study subjects will be initially asymptomatic adult women  $\geq 30$  years of age presenting for breast biopsy based on screening DBT plus standard of care diagnostic work-up.

The data from this study will be pooled with data from other subjects who will have been recruited under other GEHC protocols (including ADAPT-SCR and ADAPT-BX), for analysis described in a separate protocol (ADAPT-BIE). Figure 1 depicts the study design and procedures.

Figure 1: Study Design and Procedures

\*Images may be collected from FFDM and/or DBT performed on GE equipment prior to enrollment, if acquired within 30 days of each other.

\*\* If rebiopsy is not recommended or if histopathology remains discordant with imaging findings after rebiopsy, the subject will be withdrawn from the study.

#### 6.1.2. Study Design Details:

Open-Label

Interventions are known to researchers and subjects

Blinded

Double-Blinded

Single-site	
Multi-site	 Data will be pooled from at least 3 studies (ADAPT-SCR, ADAPT-BX as well as this enrichment protocol) occurring at multiple sites.
Randomization Procedure:	
Not randomized:	 Treatments occur as clinically indicated, not according to randomization
Single arm	
Comparator	 Diagnostic accuracy of DBT vs FFDM will be assessed in a separate protocol (ADAPT-BIE)
Crossover	 This is a within-subject crossover study
Prospective	 Subjects are enrolled and then undergo study procedures

## 6.2. Study Timeframe

The study is expected to begin in late 2015, and last for approximately two years (24 months), or until the target subject population is enrolled or the Sponsor otherwise indicates in writing that enrollment should be terminated. The end of the study shall be defined as the date when the last subject undergoes biopsy procedures and concordance is established, if applicable. Subject participation will be from the point of enrollment until truth determination of cancer status. The Investigator shall not begin the study until the applicable EC/IRB and necessary regulatory authority approvals, when required, have been obtained.

## 6.3. Controls and Minimization of Bias

The following bias control methods are being employed in this study:

- a. Selection bias: In an effort to reduce the bias introduced by ADAPT-BX subjects who are expected to be referred for biopsy based primarily on FFDM screening, ADAPT-Enrich aims to enroll cancer cases reaching biopsy through a DBT screening program.
- b. Spectrum bias will be limited by using a population expected to be representative of the general population at the investigational site, without regard for race or ethnicity.

# 7. STUDY SUBJECTS

## 7.1. Number of Subjects

Up to 200 subjects referred for breast biopsy (with an enrollment ceiling per site of 120 subjects) will be enrolled in this recruitment plan from up to two (2) centers located in the US until approximately 70 histopathology-confirmed cancers have been accrued. Sample size is determined by the need to accrue at least 120 cancer cases and 250 non-cancer cases for the overall GE Healthcare (GEHC) DBT program (ADAPT-BIE). This protocol will enroll at least one-quarter of the required cancer cases from a DBT screening environment to enrich the other cancer cases enrolled from a predominantly FFDM screening environment, thus providing cases

representative of a clinical screening population. Enrollment will be closed once the required number of cancers has been histologically identified. Data will be pooled with other sources to achieve the target number of positive and negative cancer cases, as described in Section 10.1.1 Sample Size Justification.

## 7.2. Subject Population

Study subjects will be adult women ( $\geq 30$  years of age) clinically referred for breast biopsy due to abnormalities on routine screening Digital Breast Tomosynthesis (DBT); subjects must have been asymptomatic at the time of screening.

## 7.3. Protection of Vulnerable Subjects

This study does not intend to enroll vulnerable subject populations.

## 7.4. Procedures for Enrollment

All subjects must satisfy all the inclusion criteria and none of the exclusion criteria defined in the protocol. Subjects must sign and date the informed consent form prior to completing protocol specific procedures. The Investigator may discuss with the Sponsor any subject who does not strictly meet the inclusion/exclusion criteria but who is thought to be otherwise appropriate for the study; if the Sponsor and Investigator agree that inclusion of the subject would not affect the scientific or ethical aspects of the study, the Sponsor may provide a written exception for the subject. In this case, the details of the exception will be recorded on the Case Report Form (CRF). A subject will be considered enrolled when determined eligible and informed consent is signed, whether or not the subject undergoes study procedures.

## 7.5. Inclusion Criteria

Subjects may be included that meet the following criteria:

1. Women aged 30 years or older ( $\geq 30$  years old);
2. Initially asymptomatic women who underwent routine bilateral screening with Digital Breast Tomosynthesis (DBT), followed by diagnostic work-up showing one or more abnormalities and referred for breast biopsy;
3. Are able and willing to comply with study procedures;
4. Have signed and dated the informed consent form;
5. Documented as non-pregnant based on the investigator's medical judgment and in consideration of local clinical practice standards for evidence of non-pregnancy.

 Subjects who had screening DBT or screening/diagnostic FFDM imaging on non-GE equipment may be enrolled if they agree to undergo repeat imaging on a GE system; If the prior screening and diagnostic mammographic examinations were not conducted at the recruiting site, review of those images by the investigator must confirm that breast biopsy recommendation is warranted and GE access to the images in DICOM format must be granted.

 Screening FFDM and DBT image acquisitions must be within 30 days of each other.

## 7.6. Exclusion Criteria

Subjects must be excluded from participating in this study if they meet any of the following criteria:

1. Have been previously included in this study, ADAPT-SCR recruitment plan or ADAPT-BX recruitment plan;
2. Have undergone diagnostic or surgical intervention(s) or procedure(s) on either breast, including mastectomy and cytopunction, before study-related imaging;
3. Have breasts too large to be adequately positioned on 24 x 31 centimeter (cm) DBT or FFDM digital receptor without anatomical cut-off during a DBT or FFDM examination;
4. Have participated in (within the prior 30 days) another trial of an investigational product expected to interfere with study procedures or outcomes;
5. Have breast implant(s);
6. Have reconstructed breast(s).

## 7.7. Screening Subjects for Enrollment

Subjects will be screened for recruitment from initially asymptomatic populations referred for breast biopsy due to imaging findings at each site, in accordance with local EC/IRB recruitment policy. Enrollment decisions will be based upon the Investigator's judgment. Final subject screening will include confirmation that each subject meets all inclusion and no exclusion criteria. All screening will be conducted in compliance with applicable laws, regulations, and standard procedures at the investigational site.

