### 8.2. Digital Breast Tomosynthesis (DBT) and Full Field Digital Mammography (FFDM) Examinations

Prior screening DBT and screening/diagnostic FFDM images will be collected from each subject's medical record. If prior screening and/or diagnostic images/views are not available or were not collected with GE equipment, a subject will undergo study-specific DBT and/or FFDM imaging, as needed. Study-specific imaging may include bilateral 2-view (CC/MLO) FFDM and/or DBT (as needed) performed using GE systems available at the site and according to the site's standard procedures.

Two-view DBT and two-view FFDM image acquisition (both CC and MLO views) on GE equipment shall be performed within 30 days of each other, regardless if FFDM or DBT was performed before or after the patient agreed to participate in the study. Subjects requiring study-specific imaging will undergo the following procedures:

- Enter a changing room to prepare for their mammogram;
- Each subject of child-bearing potential shall wear a lead apron or have equivalent shielding during the DBT and/or FFDM procedures;
- Undergo DBT and/or FFDM procedure(s);
- Will be monitored for AEs and SAEs from study-specific DBT and FFDM and will be recorded in the source document and CRF. Device malfunctions shall be sent to the Sponsor as per Section 12.5 Management of Device Complaints.

All scanning should be performed within the standard range of scan parameters, as per the manufacturer-provided operator's manual(s) for GE FFDM and DBT devices. The scan operator should conduct DBT and FFDM exams according to the standard clinical practice at the site with consideration for:

- Subjects with large breasts, because perspiration under the breast can cause the skin to soften, and become paper-thin;
- Any existing condition that may cause unusual discomfort or tearing of the skin, which could include telling the subject the importance of correct positioning. The subject should be positioned carefully to avoid any discomfort to abnormalities such as warts, scarring, or skin which is not intact;
- Warmth of the breast support surface, which can be warm to the touch, as it contains electronic components that generate heat;
- Positioning the breast properly in FFDM and DBT in the CC position, where it is essential that the breast is lifted away from the chest wall and gently pulled forward, in order to visualize the maximum amount of breast tissue.

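### Enrollment rests on investigator judgment when both image sets may already have been seen, with no consecutive-approach rule, no log of eligible women passed over and no express bar on a known biopsy result

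*Combined protocol and SAP*

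**What the plan says.** **How women are chosen.** Section 7.7: "Enrollment decisions will be based upon" the investigator's judgment. A separate sentence follows: "Final subject screening will include confirmation that each subject meets all inclusion and no exclusion criteria." Judgment therefore acts on top of the criteria. Section 7.4 adds a second discretionary route, a written sponsor exception for a woman who does not strictly qualify.

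**When the images exist.** The Figure 1 footnote in 6.1.1: "Images may be collected from FFDM and/or DBT performed on GE equipment prior to enrollment, if acquired within 30 days of each other." Section 8.2 applies the 30-day window "regardless if FFDM or DBT was performed before or after the patient agreed to participate in the study." For examinations done elsewhere, footnote 1 of 7.5 requires that "review of those images by the investigator must confirm that breast biopsy recommendation is warranted."

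**What is claimed about bias.** Section 6.3 offers this study as a way to reduce the selection bias from FFDM-driven referrals in ADAPT-BX. It also says: "Spectrum bias will be limited by using a population expected to be representative of the general population at the investigational site," with no restriction by race or ethnicity. It gives no sampling rule.

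**What is recorded.** The Enrollment Log in 15.2 covers enrolled women; the consecutive order mentioned there concerns their ID numbers. Section 10.1.3 summarizes women enrolled, imaged and withdrawn.

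**The concern.** The person deciding whom to enroll may already know how the lesion looks on both modalities that will later be compared. If some eligible women are approached and others are not, and the choice is related to lesion appearance, the enrolled cancers and non-cancers are no longer a fair sample of the site's DBT-recalled biopsy referrals. ADAPT-BIE can draw only on the women enrolled here, so it cannot recover those passed over. Without a record of them, nobody can check whether the enrolled set is representative.

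A related gap concerns the biopsy result. If a woman could be consented after her histology is known, selection could act on the truth itself as well as on appearance.

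**Working it through.** **1. The plan's own figures (10.1.1, 7.1).**
- Expected cancers: 200 × 0.33 = 66. This reproduces the stated 66.
- Minimum contribution: one quarter of 120 = 30.
- Share of the 120 required cancers: 30/120 = 25%; 66/120 = 55%; 70/120 = 58%.
- Against the planned total from all three protocols (66 + 90 + 6 = 162), the expected share is 66/162 = 41%.

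The cases from this study are therefore a material part of the pooled set on any reading.

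**2. Can both image sets be seen before the enrollment decision?** Yes. The 6.1.1 footnote and 8.2 allow either or both to predate consent. Footnote 1 of 7.5 makes the investigator's review of outside images a condition of entry.

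**3. Does any section limit who is approached among eligible women?** No. Section 7.7 gives judgment plus criteria, 15.2 numbers those already enrolled, and 10.1.3 reports only those enrolled. Section 6.3 states an expectation of representativeness without a procedure to secure it.

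**4. Is enrollment placed before histology?** By implication, yes:
- Table 1 lists consent before study imaging and histopathology after it.
- 6.1.2 describes enrollment first, then study procedures.
- 6.2 runs participation from enrollment to truth determination.
- 8.3.1 treats the biopsy as still planned at entry.
- 15.1 names only mammography as data from before consent.

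**5. Is that order secured by an eligibility rule?** Take a woman with both GE image sets on file.
- She needs no study-specific imaging (8.2), so the order in Table 1 has no imaging step to attach to.
- Section 7.4 requires consent before protocol-specific procedures, but her biopsy proceeds under standard of care (8.4).
- Exclusion 2 bars breast procedures before study-related imaging, and hers is complete.
- Inclusion 2 sets no interval between biopsy referral and consent.

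No criterion expressly excludes her if she is consented after her result is known.

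**6. Accrual pressure.** Under a binomial model with n = 200 and p = 0.33:

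| Cancers reached | Probability |
|---|---|
| at least 30 | above 0.9999 |
| at least 60 | 0.84 |
| at least 66 | 0.53 |
| at least 70 | 0.30 |

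At 33%, 70 cancers need 70/0.33 ≈ 212 women against a cap of 200. The target is worded as approximate, so the 0.30 should not be read as the chance of success.

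**7. How a selection shift would carry through (illustration; the shift is assumed).** If selection moved the share of some lesion type among this study's cancers by d points, and the other cancers were unaffected, a pooled set of 120 would move by (share) × d, with share from 25% to 58%. For d = 5, 10 and 20 points this gives 1.3 to 2.9, 2.5 to 5.8 and 5.0 to 11.7 points. The documents give no value for d.

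**The case against.** The strongest reply is that judgment is bounded. Every woman must meet fixed criteria, and some of those need judgment anyway: ability to comply, non-pregnancy, and confirmation of an outside biopsy recommendation. Nothing in 7.7 invites choice by lesion appearance. This stands as a limit on the concern, but confirming eligibility does not decide which eligible women are approached.

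Second, this study tests no hypothesis (5.1). The comparison belongs to ADAPT-BIE, whose case-selection rules are not in these documents and could limit or compound the problem. Each woman also contributes both modalities, so selection on general suspicion need not favor either. This stands, and it is why no direction or size can be claimed.

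Third, 15.4 mentions site study logs and 16.2 a separate monitoring plan, so a screening log may exist outside the protocol. That is possible, but the protocol neither requires it nor reports from it.

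Some stronger readings are tempting but not supported:
- A reader might infer that women with known histology may freely enter. The sections listed in step 4 of the working point the other way; the gap is only the lack of an express criterion.
- A reader might see a contradiction between 7.7 and 6.3. Section 6.3 promises no consecutive sampling, so 7.7 leaves its aim unsupported and does not conflict with it.
- A reader might take the 0.30 probability as a strong motive to hand-pick obvious cancers. The target is approximate, the floor is 30, and the Appendix D rationale says the combined targets were set high on purpose to allow for attrition and slow ADAPT-BX enrollment. Section 10.4 does define success by meeting accrual targets, so some pressure exists, but nothing shows that selection occurs.

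**Conclusion.** The point holds in a limited form. Section 7.7 leaves the choice among eligible women to judgment at a time when both image sets may have been seen. No consecutive-approach rule or log of non-enrolled women backs the aims in 6.3. Consent before histology is implied but is not an eligibility rule.

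This could bias the case mix passed to ADAPT-BIE, to which this study contributes 25% to 58% of the 120 required cancers (30 to about 70). Those percentages assume a pooled set of exactly 120. A reader might go on to infer that the bias favors DBT. The documents do not support that: the accrual target would favor plainly suspicious cancers, which may be visible on both modalities, and no figure is given for cancers poorly seen on FFDM. Neither the direction nor the size of any bias can be determined.

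The change is worth making because it is cheap during enrollment and the women passed over cannot be recovered afterwards.

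**What to change.** - **7.7:** replace the judgment sentence with: *All consecutive women at the site who meet the criteria will be invited until enrollment closes; consent must be signed before any histopathology result from the index biopsy is known.* The second clause makes explicit the order that Table 1 implies.
- **15.2:** extend the Enrollment Log to eligible women not enrolled, with the reason for each.
- **10.1.3:** report those counts and reasons by site.

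A log allows representativeness to be checked. It does not allow the sample to be corrected afterwards, because the missing women's images are not recovered.

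The cost is protocol wording, some coordinator time, and possibly a slightly lower cancer yield than hand-picking would give. The 200-subject cap, the 66 expected cancers and the endpoints stay as they are.
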